# 6.2.5. Duration of Response

DOR is defined, for participants with an objective response per IMWG criteria, as the time from the first documentation of objective response that is subsequently confirmed, until confirmed PD per IMWG criteria, or death due to any cause, whichever occurs first. It will be calculated as follows:

DOR (months) = [date of event or censoring – first date of objective response + 1] / 30.4375

The censoring rules for DOR are as described for PFS in Section 6.2.4, except that participants will not be censored for no adequate post-baseline assessment, as only participants with an objective response are included in the analysis of DOR.

If at least 3 participants achieve an objective response and subsequently have an event, DOR will be estimated using the same Kaplan-Meier method as described for PFS in Section 6.2.4 and displayed graphically where appropriate. Otherwise only listings will be provided.

The DOR rate at 3, 6, 9, and 12 months (and in subsequent 6-month increments while there are participants still at risk) will be estimated with corresponding two-sided 95% CIs.

In addition, duration of response follow-up from initial dose and initial response will be summarized with simple descriptive statistics and a swimmer plot for DOR may also be produced.

DOR by BICR and DOR by investigator will be summarized separately.

If  $\geq$ 5% of responders have died due to COVID-19 related reasons, these participants will be censored at the time of death and be counted as a competing risk event in a supplementary cumulative incidence analysis.

# 6.2.6. Duration of Complete Response

DOCR is defined, for participants with a sCR/CR per IMWG criteria, as the time from the first documentation of sCR/CR that is subsequently confirmed, until confirmed PD per IMWG criteria, or death due to any cause, whichever occurs first. It will be calculated as follows:

DOCR (months) = [date of event or censoring – first date of sCR/CR + 1] / 30.4375

The censoring rules for DOCR are as described for DOR in Section 6.2.5.

If at least 3 participants achieve a sCR/CR and subsequently have an event, DOCR will be estimated using the same Kaplan-Meier method as described for DOR in Section 6.2.5 and displayed graphically where appropriate. Otherwise only listings will be provided.

The DOCR rate at 3, 6, 9, and 12 months (and in subsequent 6-month increments while there are participants still at risk) will be estimated with corresponding two-sided 95% CIs.

DOCR by BICR and DOCR by investigator will be summarized separately.

If  $\geq$ 5% of responders have died due to COVID-19 related reasons, these participants will be censored at the time of death and be counted as a competing risk event in a supplementary cumulative incidence analysis.

# 6.2.7. Overall Survival

OS is defined as the time from the date of first dose until death due to any cause and will be calculated in months as follows:

OS (months) = [date of death or censoring - date of first dose +1] / 30.4375

Survival status is expected to be collected irrespective of study intervention discontinuation or participant's request to discontinue study procedures. All participants who have not withdrawn consent for further participation in the study should be followed for survival until the end of the study. OS for participants not known to have died are censored on the date of last known alive.

OS time will be estimated using the same Kaplan-Meier method and displayed graphically as described for PFS in Section 6.2.4. Median OS and 2-sided 95% CI will be provided. The OS rate at 12, 24, and 36 months (and in subsequent 12-month increments while there are participants still at risk) will be estimated with corresponding two-sided 95% CIs.

Frequency (number and percentage) of participants with death events and censoring reasons will be presented by cohort along with the overall event and censor rates. The event and censoring reasons are as follows:

- Death;
- Ongoing and no death;
- Withdrawal of consent;
- Lost to follow-up.

The OS time or censoring time and the reasons for censoring will also be presented in a listing.

In addition, duration of follow-up time will be summarized with simple descriptive statistics, as well as with reverse Kaplan-Meier method.

# 6.2.8. Time to Response

TTR is defined, for participants with an objective response per IMWG criteria, as the time from the date of first dose to the first documentation of objective response that is subsequently confirmed. For participants with EMD at baseline, MR or better (for those with target plasmacytomas) and CR or better (for those with non-target non-bone EMD only) cannot be confirmed until a post-baseline EMD assessment is performed and the date of confirmed response cannot be prior to the initial EMD assessment date. TTR will be calculated in weeks as follows:

TTR (weeks) = [date of first objective response – date of first dose + 1] / 7

Time to VGPR (TTVGPR) and time to CR (TTCR) are defined similar to TTR but for participants with BOR of VGPR or better and sCR/CR, respectively.

TTR, TTVGPR, and TTCR will be summarized using simple descriptive statistics.

TTR, TTVGPR, and TTCR by BICR and TTR, TTVGPR, and TTCR by investigator will be summarized separately.

# 6.2.9. Minimal Residual Disease Negativity Rate

MRD negativity rate is defined as the proportion of participants with negative MRD (assessed by central lab) per IMWG sequencing criteria by bone marrow aspirate (BMA) from the date of first dose until confirmed PD, death or start of new anticancer therapy, whichever occurs first.

MRD negativity will be defined by two thresholds,  $10^{-5}$  and  $10^{-6}$  (if applicable).

The MRD negativity rate will be calculated along with the 2-sided 95% CI using the Clopper-Pearson method as follows:

- MRD negative with confirmed sCR/CR based on the Safety Analysis Set;
- MRD negative based on the subset who achieved confirmed sCR/CR in the Safety Analysis Set;
- MRD negative based on the subset who achieved confirmed sCR/CR among evaluable patients who have at least one MRD assessment.

Additional subgroups may be summarized if applicable.

# 6.3. Other Secondary Endpoints

#### 6.3.1. Pharmacokinetic/Pharmacodynamics

Pharmacokinetic analyses will be based on the PK Analysis Set.

A listing of elranatamab concentrations by study visit and timepoint will be generated.

Summary statistics will be provided for pre-dose and post-dose elranatamab concentrations at scheduled visits and nominal timepoints. Values below the limit of quantitation will be treated as zero in the descriptive statistics calculations. For additional details on handling missing and BLQ values, please refer to Section 5.3.1. The summary table will include the number of participants, number of samples with BLQ values, mean, standard deviation, percent coefficient of variation (%CV), median, minimum, maximum, geometric mean, and geometric %CV. For this summary, samples that meet the following conditions will be included:

- For pre-dose samples, have the sample collected before the next dose administration,
- For the 6-hour and 24-hour post-dose samples, have the sample collected within  $\pm$  25% of the nominal scheduled time,
- At least 2 consecutive planned doses were administered without interruption or reduction prior to trough sample collection,
  - Ex. C1D8 predose is included in the summary if C1D1 and C1D4 were administered as planned (ie, 12 and 32 mg, respectively),

• Ex. C1D15 predose is included in the summary if C1D4 and C1D8 were administered as planned (ie, 32 and 76 mg, respectively).

Box and Whiskers plots of elranatamab trough concentrations after multiple doses for participants from the PK Analysis Set who meet the conditions stated above will be presented by study visit. The Box and Whiskers plots will be overlaid with geometric means.

In addition, the PK data from this study may be combined with PK data from other studies to develop a population PK model. The correlation between elranatamab exposure parameters and pharmacodynamic biomarker, efficacy and/or safety outcomes will be explored if data allow. Details of these modeling analyses are not within the scope of this SAP and will be described in a separate population PK and exposure response analysis plan.

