6.1. Study Intervention(s) Administered

6.1.1. Administration

Qualified and trained investigator site personnel will administer elranatamab to participants by SC injection. Ideally, each injection may be up to 2 mL in volume; however, if the maximum volume allowed per institution's policy is lower than 2 mL, the number of injections may be increased to accommodate this difference in volume and ensure the correct dose is delivered.

Elranatamab should be administered to the abdomen, with preference given to the lower quadrants when possible. Refer to Appendix 9 for details on administration of multiple

injections to the abdomen. Study staff should refer to the IP Manual for specific instructions on the handling, preparation, and administration of study intervention.

Participants will receive elranatamab as a SC injection administered QW on Days 1, 8, 15 and 22 of each 28-day cycle. Elranatamab is also administered on C1D4. A minimum of 2 days should be maintained between the 2 step-up priming doses (C1D1 and C1D4), a minimum of 3 days between C1D4 dose and the first full dose (C1D8); a minimum of 6 days should be maintained between doses thereafter. If a participant has received QW dosing for at least 6 cycles and has achieved an IMWG response category of PR or better persisting for at least 2 months, the dose interval will be changed from QW to Q2W (eg, beginning C7D1) (see Section 6.6.3).

Dose modifications may occur according to the guidelines described in Section 6.6.

The first doses of study intervention will be 12 mg (C1D1) and 32 mg (C1D4), which will serve as priming doses and will be administered on an inpatient basis. Participants are required to be hospitalized and monitored for CRS/ICANS for at least 2 days (~48 hours) beginning on C1D1, and for 1 day (~24 hours) for C1D4. Hospitalization up to 5 days from C1D1 to C1D5 inclusive may be considered.

The dose of elranatamab should be increased to 32 mg on C1D4 and to 76 mg on C1D8 as long as the participant meets the redosing criteria listed in Section 6.6.1. If a participant does not meet these criteria on C1D4 and C1D8, dosing should be deferred until the criteria are met.

For both the priming doses and first full dose (76 mg), premedication for CRS is required (see Section 6.5.1)

Each participant may receive study intervention until confirmed disease progression, unacceptable toxicity, withdrawal of consent, or study termination.

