9.4.3.2. Pharmacokinetic Analyses

PK data analyses will include descriptive summary statistics of the pre-dose and post-dose serum concentrations of elranatamab by study visit and time point. In addition, the PK data from this study may be used to develop a population PK model. The correlations between elranatamab exposure parameters and pharmacodynamic biomarker, efficacy and/or safety outcomes will be explored if data allows. The results of these modeling analyses will be reported separately from the clinical study report.

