#### 2.2. Study Objectives, Endpoints, and Primary Estimand

Туре	Objectives	Endpoints
	Primary	
Efficacy	To determine the efficacy of Elranatamab in Cohort A and Cohort B	• ORR by BICR per IMWG.
	Key Seconda	iry
Efficacy	• To determine additional efficacy of Elranatamab in Cohort A	ORR by BICR baseline EMD status per IMWG.
	Secondary	7
Efficacy	To determine additional efficacy of Elranatamab in Cohort A and Cohort B	
 
DOR by BICR and investigator per IMWG.
 
CRR by BICR and investigator per IMWG.
 
ORR by investigator per IMWG.
 
DOCR by BICR and investigator per IMWG.
 
PFS by BICR and investigator per IMWG.
 
OS.
 
TTR by BICR and investigator per IMWG.
 
MRD negativity rate (central lab) per IMWG.
 

Safety	• To determine the safety and tolerability of Elranatamab	
 
AEs and laboratory abnormalities as graded by NCI CTCAE v5.0.
 
Severity of CRS and ICANS assessed according to ASTCT criteria.
 

РК	• To evaluate the PK of Elranatamab	• Pre- and postdose concentrations of Elranatamab.
Immunogenicity	• To evaluate the immunogenicity of Elranatamab	• ADAs and NAbs against Elranatamab.

Туре	Objectives	Endpoints
	Explorator	y
Efficacy	To explore additional efficacy of Elranatamab in Cohort A and Cohort B	• sMRD-negativity, DOMRD negativity, and biochemical response rate.
Biomarker	• To explore the relationship between Elranatamab and the biology of the participant's MM	• Measurements of biomarkers (DNA, RNA, protein or defined cell types) resulting from analyses of peripheral blood, saliva and/or BM biospecimens.
	• To explore correlations between Elranatamab exposure and efficacy, safety and biomarker endpoints, if data allow	• Selected PK, efficacy, safety and biomarker endpoints.
PRO	• To assess the impact of elranatamab on patient-reported symptoms and functioning	
 
EORTC QLQ-C30 and MY20.
 
EORTC QLQ CIPN20.
 
EQ-5D.
 
PGIS/PGIC.
 

	• To collect healthcare resource use data	• Hospitalizations, including length of stay, ICU admissions, transfusions, infections and outpatient visits.

**Primary Estimand**: The treatment effect of elranatamab on objective response rate (ORR) as assessed by blinded independent central review (BICR) per the International Myeloma Working Group (IMWG) criteria. The estimand has the following attributes:

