#### 6.6.3.1. Dose Reductions, Interruptions, and Delays

A dose reduction is defined as a nonzero dose that is less than the planned and previous non-zero dose. The planned dose is the same as the prior dose except for C1D4 and C1D8.

The number and percentage of participants with at least 1 dose reduction as well as a breakdown of dose reductions  $(1/2/3/ \ge 4)$  will be summarized by cohort. In addition, the number and percentage of participants with at least 1 dose reduction due to AE will also be summarized.

An interruption is defined as a continuous missed scheduled dose based on the planned dosing frequency (QW or Q2W). The number and percentage of participants with dose interruptions as well as a breakdown of dose interruptions  $(1/2/3/\geq 4)$  will be summarized by cohort and overall. In addition, the number and percentage of participants with at least 1 dose interruption due to AE will also be summarized. Percentages will be calculated based on the total number of participants in the Safety Analysis Set.

A dose delay will be derived based on study drug administration date and will be grouped into the following categories based on the deviation of the actual to the planned treatment administration day (relative to the previous treatment administration date):

- No delay;
- 1-3 days delay;
- 4-6 days delay;
- 7 or more days delay (only in the Q2W schedule).

The number and percentage of participants with delayed study drug administration and maximum length of delay, ie, the worst case of delay if participants have multiple dose delays will be summarized by cohort, as applicable.

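### From C10D1 on, the PK trough tables and box plots pool weekly and two-weekly dosing, so no Q2W trough is summarised and the planned switch itself would appear as falling exposure

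*SAP*

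**What the plan says.** The SAP lists the PK endpoint as secondary: "Pre- and postdose concentrations of Elranatamab" (section 2.2). Protocol 9.4.3.2 summarises "serum concentrations of elranatamab by study visit and time point". SAP 6.3.1 does the same: "Summary statistics will be provided for pre-dose and post-dose elranatamab concentrations at scheduled visits and nominal timepoints". Its trough box plots, for participants "who meet the conditions stated above will be presented by study visit", carry geometric means as an overlay. Neither document names dosing interval as a stratum for PK.

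A trough enters the summary on this condition: "At least 2 consecutive planned doses were administered without interruption or reduction prior to trough sample collection". There is no condition on days since the last dose.

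On dosing, Protocol 6.1.1 says that for a participant with at least six QW cycles and a PR or better persisting for at least 2 months, "the dose interval will be changed from QW to Q2W (eg, beginning C7D1"). SAP 5.2.5 and 6.6.3 also provide for a return to weekly dosing. The Schedule of Activities takes pre-dose PK samples on C2D1, C3D1, C4D1, C7D1, C10D1 and every third cycle after that. All scheduled 6 h and 24 h post-dose samples fall in Cycle 1.

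**The concern.** The switch is part of the design and depends on response. The mix of regimens at each late visit is therefore neither fixed nor random, and it can change again as participants return to QW. A visit mean that combines 7-day and 14-day troughs describes neither regimen. Read along the visit axis, it would tend to drop after C7D1 even if nobody's clearance changed. ADA is sampled at the same visits, and SAP 6.3.2 may explore its effect on PK, so a drop caused by the schedule could be misread as an ADA or time effect.

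Protocol 4.3 justifies Q2W on the ground that a lower dose intensity may be enough to hold a response. No planned SAP table or plot shows the exposure reached at that intensity. The SAP does split ORR (6.1.3) and TEAEs (6.7.1) by the switch, so the missing split for PK looks like an oversight.

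**Working it through.** The PK objective has no stated sample size, power or alpha, so there is no plan figure to reproduce. The check has four parts.

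**1. First affected visit.** Six QW cycles must come first, so Q2W dosing starts at C7D1 at the earliest. The C7D1 pre-dose sample follows the C6D22 dose and is a 7-day trough for everyone. At C10D1, a QW participant was last dosed on C9D22 (7 days earlier). A Q2W participant with two evenly spaced doses per cycle was last dosed on C9D15 (14 days earlier). C10D1 is thus the first scheduled pre-dose visit that can mix intervals.

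**2. Does the inclusion condition separate them?** No. SAP 6.6.3.1 judges an interruption against the participant's own planned frequency, QW or Q2W, so an uninterrupted Q2W participant passes.

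**3. Dose rate (SAP 6.6.3).** QW: 76 × 4 = 304 mg per cycle, or 76 mg/week. Q2W: 76 × 2 = 152 mg per cycle, or 38 mg/week. The planned rate halves.

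**4. Size at C10D1.** Assumptions, none of them given in the documents: one compartment, linear kinetics, constant clearance, bolus-like input, QW at steady state by C7D1, switch exactly at C7D1, half-life h of 10 to 30 days.

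- Fraction remaining after 7 days: x = 2^(−7/h).
- Steady-state Q2W/QW trough ratio: s = x/(1+x).
- Share of the transition still outstanding after 84 days: e = x^12 = 2^(−84/h).
- Ratio at C10D1: r = s + (1 − s)·e.
- Pooled arithmetic mean below QW, with share f on Q2W: f·(1 − r).

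| h (days) | x | s | e | r | f = 0.5 | f = 0.8 |
|---|---|---|---|---|---|---|
| 10 | 0.616 | 0.381 | 0.003 | 0.383 | 31% | 49% |
| 14 | 0.707 | 0.414 | 0.016 | 0.423 | 29% | 46% |
| 21 | 0.794 | 0.442 | 0.063 | 0.477 | 26% | 42% |
| 30 | 0.851 | 0.460 | 0.144 | 0.537 | 23% | 37% |

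For h = 30: r = 0.460 + 0.540 × 0.144 = 0.537; 0.5 × 0.463 = 23%; 0.8 × 0.463 = 37%. Using s in place of r would overstate the C10D1 deficit at long half-lives, because 14% of the shift has still to occur.

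Superposing the actual dose sequence (12, 32, then 76 mg) gives 0.383 at 10 days and 0.536 at 30 days, in agreement. Widening the half-life to 5 to 35 days moves r to 0.275 to 0.564. For the geometric means drawn on the box plots, the deficit is 1 − r^f: 27% to 38% at f = 0.5 and 39% to 54% at f = 0.8, for half-lives of 30 and 10 days respectively.

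**Which dose counts as planned?** SAP 6.6.3.1 says "The planned dose is the same as the prior dose except for C1D4 and C1D8". On that reading, repeated 44 mg or 32 mg doses are planned and are not new reductions, so their troughs could join the 76 mg row. The examples in SAP 6.3.1 and the planned dose in 6.6.3 instead use protocol doses, which would exclude them. The text does not say which meaning governs the PK filter.

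**The case against.** The strongest reply is that little is lost. Every scheduled visit through C7D1 precedes the switch, so C2D1, C3D1, C4D1 and C7D1 describe weekly dosing, and the scheduled post-dose samples all lie in Cycle 1. This stands. A reader might infer that the PK objective can describe neither regimen; the sampling schedule does not support that. The loss is the Q2W trough and the late QW trough.

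A reader might also infer that reduced-dose samples are bound to enter the 76 mg row. That does not follow either. The sentence in SAP 6.6.3.1 serves to count dose reductions, and the examples in 6.3.1 point to protocol doses. What remains is an ambiguity.

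Concentrations will be listed, and a population PK model and exposure-response work may follow under a separate plan. This reduces the harm, but a listing is not a summary of a declared secondary endpoint. The model is optional and outside this SAP.

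Finally, the size of the fall is assumed. Switching depends on response, so switchers may differ in exposure from those who stay on QW, and a switch later than C7D1 leaves less of the shift complete at C10D1. This stands: the direction is expected, but the figure is not documented.

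**Conclusion.** The concern holds for trough summaries from C10D1 on. As written, the plan gives late-visit tables and plots that represent neither interval and would be expected to fall through the halved dose rate alone. Under the stated assumptions, the C10D1 Q2W trough is about 38% to 54% of the QW trough. The pooled arithmetic mean is about 23% to 31% below QW with half switched and 37% to 49% below with 80% switched. These figures rest on linear one-compartment kinetics, constant clearance, a half-life of 10 to 30 days, a C7D1 switch and an assumed share switched; the observed pattern may differ.

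This is a reporting gap in a descriptive secondary endpoint. It affects no primary or key secondary test. Dosing text next to the switch is redacted in places and is not counted as a gap.

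**What to change.** In SAP 6.3.1:

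- From C10D1 on, present trough tables and box plots separately by the dosing interval in force before the sample (QW, Q2W).
- Flag participants who returned from Q2W to QW, or show them separately. With a long half-life, their troughs have not yet re-accumulated and do not belong with continuous QW.
- State whether *planned* in the inclusion condition means the protocol dose (as in the 6.3.1 examples and 6.6.3) or the participant's prior dose (as in 6.6.3.1), so that reduced-dose samples are not mixed with 76 mg.

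The cost is SAP wording and a stratification variable that can be derived from exposure data already collected. Study conduct does not change. The drawback is fewer participants per row at late visits. SAP 5.3.1 already handles very small rows by showing only the minimum and maximum when fewer than 3 evaluable values exist.
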